2. LIST OF ABBREVIATIONS

Include a list of all abbreviations used in the TSAP

Term	Definition / description
AE	Adverse Event
AESI	Adverse Event of Special Interest
AI	Augmentation Index
AMP	Auxiliary Medicinal Product
ATS	American Thoracic Society
AUC	Area under the Curve
BAC	Benzalkonium chloride
BI	Boehringer Ingelheim
bid	bis in die (twice daily dosing)
BMI	Body Mass Index
BRPM	Blinded report planning meeting
BSA	body surface area
CABG	Coronary Artery Bypass Graft
CI	Confidence Interval
CML	Local Clinical Monitor
CMR	Cardiac Magnetic Resonance
COPD	Chronic Obstructive Pulmonary Disease
CRA	Clinical Research Associate
CRF	Case Report Form
CRO	Contract Research Organisation
CT	Computer tomography
CTC	Common Terminology Criteria
CTMF	Clinical trial master file
CTP	Clinical Trial Protocol
CTR	Clinical Trial Report
CV	Cardiovascular
DEDP	drug exposure during pregnancy
DM&SM	Boehringer Ingelheim Data Management and Statistics Manual
DMG	Dictionary Maintenance Group

Term	Definition / description
DPI	Dry Powder Inhaler
DRA	Drug Regulatory Affairs
ECG	Electrocardiography
eCRF	Electronic Case Report Form
ECSC	European Coal and Steel Community
ED	end diastolic
EDTA	Disodium edentate
EF	ejection fraction
EFL	Expiratory flow limitation
EMA	European Agency for the Evaluation of Medicinal Products
EoO	End of Observation
EoT	End of Treatment
ERS	European Respiratory Society
ERV	Expiratory reserve volume
EU	European Union
EudraCT	European Clinical Trials Database
FAS	Full Analysis Set
FC	Flow Chart
FDC	Fixed Dose Combination
FEV1	Forced Expiratory Volume in 1st second
FRC	Functional Residual Capacity
FVC	Forced Vital Capacity
GCP	Good Clinical Practice
GOLD	Global Initiative for Chronic Obstructive Lung Disease
HCG	human chorionic gonadotropin
HFA	hydrofluoroalkane
IB	Investigator's Brochure
IC	Inspiratory capacity
ICH	International Conference on Harmonisation
ICS	Inhaled corticosteroids
IEC	Independent Ethics Committee
IMP	Investigational Medicinal Product

Term	Definition / description
IRB	Institutional Review Board
IRT	Interactive Response Technology
ISF	Investigator Site File
IVC	inspiratory vital capacity
LABA	Long-acting β 2-agonist
LAMA	Long-acting muscarinic antagonists
LBBB	Left bundle branch block
LDH	Lactate Dehydrogenase
LOCF	Last observation carried forward
LPDD	Last Patient Drug Discontinuation
LV	Left Ventricle
LVEDVI	Left Ventricular End Diastolic Volume Index
LVH	Left ventricular hypertrophy
MACE	Major adverse cardiovascular event
MCID	Minimal clinically important difference
MD	Medical Degree
MDI	Metered Dose Inhaler
MedDRA	Medical Dictionary for Drug Regulatory Activities
MMI	Myocardial mass index
mMRC	Modified Medical Research Council Dyspnoea Scale
MMRM	Mixed-effects Model for Repeated Measures
MQRM	Medical Quality Review Meeting
MST	Medical Sub Team
NIMP	Non Investigational Medicinal Product
NYHA	New York Heart Association
O*C	Oracle Clinical
PD	Pharmacodynamics
PA	pulmonary artery
PDE-4	Phosphodiesterase Type 4
Pleth	Body Plethysmography
PFT	Pulmonary function testing
PK	Pharmacokinetics

Term	Definition / description
PPS	Per protocol set
PRN	pro re nata (as needed)
PSTAT	Project Statistician
PT	Preferred term
PV	Protocol violation
PWA	Pulse Wave Analysis
Q1	Lower quartile
Q3	Upper quartile
qd	quaque die (once a day)
REML	Restricted Maximum Likelihood
REP	Residual effect period, after the last dose of medication with measureable drug levels or pharmacodynamic effects still likely to be present
RV	right ventricular
RVol	Residual Volume
SA	Statistical analysis
SAE	Serious Adverse Event
SD	Standard deviation
SGOT	Serum glutamic-oxaloacetic transaminase
SGPT	Serum glutamic-pyruvic transaminase
SGRQ	St. George's Respiratory Questionnaire
SOC	System organ class
SOP	Standard operating procedures
SmPC	Summary of Product Characteristics
SMQ	Standardised MedDRA query
STORM	storage conditions for trial medication
SUSAR	Suspected Unexpected Serious Adverse Reaction
SVI	Stroke volume index
TCM	Trial Clinical Monitor
TDI	Transitional dyspnoea index
TESS	Treatment emergent signs and symptoms
TLC	Total Lung Capacity
TMF	Trial Master File
TMW	Trial Medical Writer

Term	Definition / description
ToC	Table of contents
TSAP	Trial Statistical Analysis Plan
UK	United Kingdom
US	United States

3. INTRODUCTION

As per ICH E9, the purpose of this document is to provide a more technical and detailed elaboration of the principal features of the analysis described in the protocol, and to include detailed procedures for executing the statistical analysis of the primary and secondary variables and other data.

This TSAP assumes familiarity with the Clinical Trial Protocol (CTP), including Protocol Amendments. In particular, the TSAP is based on the planned analysis specification as written in CTP Section 7 “Statistical Methods and Determination of Sample Size”. Therefore, TSAP readers may consult the CTP for more background information on the study, e.g., on study objectives, study design and population, treatments, definition of measurements and variables, planning of sample size, randomization.

SAS[®] Version 9.4 will be used for all analyses.

4. CHANGES IN THE PLANNED ANALYSIS OF THE STUDY

All analyses described in the TSAP are outlined in the CTP.

5. ENDPOINT(S)

5.1 PRIMARY ENDPOINT

Primary endpoint of efficacy will be used as described in the CTP, Section 5.1.1 “Primary endpoint”.

5.2 SECONDARY ENDPOINT(S)

5.2.1 Key secondary endpoint(s)

No key secondary endpoints were specified in the CTP.

5.2.2 Secondary endpoints

Secondary endpoints of efficacy will be used as described in the CTP, Section 5.1.2 “Secondary Endpoints”.

- All adverse events (AEs), including any clinically relevant changes/abnormalities in physical examination, vital signs, laboratory values, and electrocardiogram (ECG)

6. GENERAL ANALYSIS DEFINITIONS

6.1 TREATMENT(S)

The doses to be administered are described in Section 4 of the CTP.

This is a crossover trial consisting of a one to three-week run-in period followed by two six-week treatment periods and a three-week post-treatment period. The day after the follow-up visit will be considered the start of the post-study period in case there are any subsequent AE data we become aware of. In this study, there will be no washout between treatment periods.

In general, the first period will be considered last until 12 hours after the last intake of medication assigned for the first period, then the second period will start

For the main safety analysis, data occurring during the treatment periods and within 21 days of stop of study drug for that period will be assigned to the respective treatment for that period. Data occurring before the first drug intake date is assigned to "screening". If the next treatment period starts within 21 days of the end of the last period, data after the start of treatment for the next period will be assigned to the treatment for that period. In this trial, next treatment will be started after end of treatment of first period as soon as possible because there is no washout period planned. The last day of the first period is the day of the last intake of medication for the first period. AEs occurring at the last day of the first period will be assigned to the first period even if the medication of the evening dose already belongs to the second period. Data more than 21 days after drug stop date for a period but before the start of the next period will be assigned to washout. Data more than 21 days after the end of the last treatment period and up to and including the date of the study termination will be assigned to follow-up.

Any cases of patient being treated with the wrong study medication will be identified and summarised as an important protocol violation (PV).

- If a patient was treated with a treatment sequence different from the randomised treatment sequence throughout the on-treatment period, i.e., a patient was treated with incorrect study medication during every treatment period, this patient will be included in the treated set and will be analysed as treated for both efficacy and safety analyses, including patient disposition. Such a case will be reported as an important PV and this patient will be excluded from the per-protocol set (PPS).
- If a patient was treated with incorrect study medication throughout one treatment period only, but not both treatment periods, this patient will be included in the treated set and will be analysed as treated for safety analysis. For efficacy analysis, only efficacy data collected in the correct treatment period will be used and efficacy data collected in the other treatment period with the duplicate study medication will not be used. For patient disposition, such a patient will be analysed as randomised. Such a case will also be reported as an important PV but this patient will not be excluded from the PPS.

If a patient was treated with incorrect study medication during part of a treatment period, data of this patient will be discussed case by case at final Blinded report planning meeting (BRPM) or data base lock meeting (DBLM).

6.2 IMPORTANT PROTOCOL VIOLATIONS

A patient's deviation from the trial protocol is considered "relevant" if it can be expected that the deviation had a distorting influence on the assessment of the treatment effect on the primary endpoint of the trial or could affect the patient's safety/rights.

Table 6.2:1 gives the important protocol violations (IPVs) for the trial. The final decision with regards to important PVs and exclusion from the PPS will be made at the final blinded report planning meeting (BRPM) or data base lock meeting (DBLM).

In the case that a patient was randomised in both this trial and another trial or was randomised at two different sites in this trial, the patient will be indicated as having an important PV (IPV, see Table 6.2: 1-Exclusion Criterion 26). The following process will be followed with regards to the patient's data.

- All efficacy data will be excluded from the analysis and the patient will be excluded from the Full Analysis Set (FAS) (for this trial or both trials as appropriate).
- The only safety data which will be reported is exposure and serious adverse events (SAEs). These will be analysed according to the treatment which the patient actually received. If the patient was randomised twice in this study, the patient's data of periods with the same treatment will be combined (i.e. the patient is only counted once). If the patient participated in two different trials in the same project, he/she will be reported separately for each trial. As well, care will be taken with regard to the SAE narratives as to whether data for one patient number is relevant for an SAE under the other patient number.
- For disposition, demographics, baseline characteristics and important PVs, the patient will be analysed as treated. If the patient was randomised twice in this study and the treatments in periods are different, the patient will be counted under each treatment. A footnote will be included in the disposition table identifying the situation and noting that the patient is counted twice for disposition as well as demographics, baseline data and important PVs.

Table 6.2: 1 Important protocol violations

Category / Code	Description	Requirements	Excluded from*
A	Entrance criteria not met		
A1	Inclusion criteria not met	Inclusion Criteria 2-8 not met as specified in the protocol.	Exclude from PPS*: 2-8
A2	Exclusion criteria not met	Exclusion Criteria 1-28 not met as specified in the protocol	Exclude from PPS*: 3-8, 10-14, 16-22, 26-28
B	Informed consent		
B1	Informed consent not available/not done	Informed consent date missing; no signature on ICF.	All
B2	Informed consent too late	Date of informed consent was after the date of any study-related procedure, or a patient signed the correct version of the ICF after Visit 0. If date of informed consent equals to date of Visit 1, such cases will be discussed at MQRM/BRPM/DBL meetings.	None
C	Trial medication and randomisation		
C1	Incorrect trial medication taken	Not throughout the entire study treatment period; could be at a clinic visit or between clinic visits. External vendor will check before unblinding.	PPS (decision at BRPM)
C2	Randomisation order not followed	Throughout the study	PPS
C3	Non-compliance with study medication		
C3.1	Serious non-compliance with study medication as reported in monitoring report or issue listing (formerly manual PV spreadsheet)	Decision at BRPM/MQRM.	PPS if at Visit 3 or 4 and at respective second and third CMR assessments
C4	Medication code broken inappropriately	To be discussed and decided during MQRM/BRPM. Only inappropriate code breaks are IPVs (e.g. unblinding by Global Pharmacovigilance is not considered inappropriate code break).	PPS

Table 6.2: 1 (continued) Important protocol violations

Category / Code	Description	Example/Comment	Excluded from*
D	Concomitant medication		
D1	Improper medication washout for CMR assessment (at baseline CMR or on-treatment CMRs for primary endpoint)	Washout not met for baseline CMR assessment and for on-treatment CMRs. Decision at BRPM*	PPS
D2	Prohibited medication use during study	Check CT. Decision at BRPM.	PPS if in the week prior to Visit 2, 3, and 4
F	Incorrect timing		
F3	Primary endpoint recorded outside time window	A. With respect to treatment duration: 1) CMR < 35 days of treatment in each period B. With respect to clinic visits: 1) CMR baseline assessment at or after Visit 2 date, and/or 2) second CMR assessment after Visit 3 date, and/or 3) third CMR assessment after Visit 4 date, and/or 4) second CMR assessment < 1 hour or > 8 hours post morning dose of study medication at Visit 3 and/or 5) third CMR assessment < 1 hour or > 8 hours post morning dose of study medication at Visit 4	PPS
Z	Other		
Z1	Serious GCP non-compliance	Manual PVs reported by CML/CRA which are considered as important. Carefully reviewed, described and documented in DBL meeting minutes.	PPS
Z2	Other PV affecting efficacy and possibly safety	Additional PV identified through monitoring which impacts the primary analysis and possibly patient's rights or safety. Carefully reviewed and documented in BRPM minutes and comment field of IPV ADS.	PPS
Z3	Other PV affecting safety only	Additional PV identified through monitoring which impacts patient's rights or safety. Carefully reviewed and documented in BRPM minutes and comment field of IPV ADS.	None

KEY: CT = Concomitant Therapy, BRPM = Blinded report planning meeting, CML = Local Clinical Monitor, CRA = Clinical Research Associate, ICF = informed consent form, MQRM = Medical Quality Review Meeting, PPS = Per protocol set, DBL = Data Base Lock, ADS = Analysis Data Set

*Final decision will be discussed and determined prior to database lock.

Note: Missing visits, evaluations, and tests are considered as missing data, but not protocol deviations.

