### Respimat® and Accuhaler® inhalers return

The Respimat® and Accuhaler® dispensed for treatment periods can be used for approximately 30 days each. All used and unused trial medication must be returned to the patient treatment boxes and must be brought to the subsequent site visit by the patient. The reserve inhalers should also be returned at each clinic visit to be replaced if it has been used or primed.

All used and unused Respimat® and Accuhaler® inhalers dispensed at Visit 2 will be returned at Visit 3 at the end of first treatment period (and those newly dispensed at Visit 3 will be returned at Visit 4 respectively), after administration of morning trial medication at the site. This procedure allows for prompt recording on the drug accountability forms by the site staff and ensures that during the next treatment period trial medication of the previous treatment period could not be administered by the patient.

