### **7.7 DETERMINATION OF SAMPLE SIZE**

This is an exploratory trial and only limited data exist about LVEDVI. A cross-over study in COPD patients evaluated the effect of fluticasone furoate and vilanterol versus placebo on mean change from baseline in LVEDVI [[R16-3512](#)]. The mean difference was 3.63 mL/m^2 with a standard deviation of approximately 7.3 mL/m^2. Assuming a 2-sided alpha of 5% and a within-patient standard deviation of 7.5 mL /m^2, a sample size of approximately 74 patients would have 80% to 90% power to reject the null hypothesis if the true treatment difference is 2.5 to 3.0 mL/m^2. If the SD is 20% larger (9.0 mL /m^2), then the power would still be 80% for a treatment difference of 3.0 mL/m^2. This results in a sample size of 74 patients.

Table 7.7: 1                      Sample size for 80% and 90% power, 2-sided alpha= 0.05

Power	Difference [ml/m  ]	SD	Sample Size
80%	3.0	7.5	52
90%	3.0	7.5	68
80%	3.0	9.0	74
90%	3.0	9.0	98
80%	2.5	7.5	74
90%	2.5	7.5	98

Calculations were performed using nQuery Advisor® 7.0 statistical package by Statistical Solutions Ltd.

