7.4 PRIMARY ENDPOINT(S)

In the primary analysis, the two-sided hypothesis as given in Section 7.2 in the CTP will be tested based on adjusted mean change from baseline in LVEDVI, as listed in Section 5.1.1 in the CTP, using a restricted maximum likelihood (REML)-based MMRM. This model will include treatment and period as fixed effects, patient as a random effect and baseline as covariate. Unstructured covariance structure will be used for within patient variation. If convergence is not achieved, the compound symmetry covariance structure will be used. The SAS procedure MIXED will be used involving the restricted maximum likelihood estimation and the Kenward-Roger approximation for denominator degrees of freedom. This approach is described in [\(2\)](#). Adjusted mean values as well as treatment contrasts will be presented together with the 95% confidence intervals (CI) and p-values. The primary analysis will be performed on FAS-EE.

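### A CMR scan dated after Visit 3 or Visit 4 is barred only from the per-protocol set, so as written it can enter the primary FAS-EE analysis under the treatment just finished

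*SAP*

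**What the plan says.** **Mistimed scans.** SAP 6.2, Table 6.2:1, row F3 covers primary-endpoint values recorded outside their window. Its clinic-visit conditions include "2) second CMR assessment after Visit 3 date, and/or 3) third CMR assessment after Visit 4 date". The exclusion column for the row names the PPS and nothing else.

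**Analysis sets.** SAP 7.4 states: "The primary analysis will be performed on FAS-EE". SAP 6.3 forms FAS-EE from the FAS by removing data from patients who had an exacerbation; scan timing plays no part. Table 6.3:1 assigns analyses to the treated set and FAS-EE only. SAP 6.3 also says that FAS membership is decided after any rules that set values to missing have been applied.

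**Missing-data rules.** SAP 6.6 sets spirometry and plethysmography values to missing after rescue use. For CMR it says only that nothing is imputed.

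**Endpoint and treatment change.** Protocol 5.1.1 takes the LVEDVI value from the week before Visit 3 or 4. Flow Chart footnote 11b and Protocol 6.1 also allow a scan on the visit day. The last dose of each period is the clinic morning dose on that day, after which all of that period's medication is collected. Protocol 4.1.4.2 says this "ensures that during the next treatment period trial medication of the previous treatment period could not be administered by the patient". There is no washout. SAP 6.1 adds that in general "the first period will be considered last until 12 hours after the last intake of medication assigned for the first period".

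**The concern.** The SAP foresees these scans, calls them important violations, and then attaches a consequence that does not reach the primary analysis. A second scan dated after Visit 3 is made once the first treatment has been withdrawn and the second is starting, yet it would be analysed as the six-week value of the first. A third scan dated after Visit 4 is made after trial treatment has stopped, yet it would be analysed as the six-week value of the second.

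The first kind pulls a patient's treatment difference towards zero. The second kind lowers whichever treatment came last. Both bear on the trial's one primary contrast.

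The SAP already accepts the opposite principle elsewhere. Under SAP 6.1, if a patient receives the wrong medication throughout one period, efficacy data from that period are not used.

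**Working it through.** **Inputs.** Protocol 7.7 gives "Assuming a 2-sided alpha of 5% and a within-patient standard deviation of 7.5 mL"/m², 80% to 90% "power to reject the null hypothesis if the true treatment difference is 2.5 to 3.0" mL/m², and "This results in a sample size of 74 patients". For the cited cross-over study of an inhaled corticosteroid/LABA combination against placebo it reports "The mean difference was 3.63 mL/m"². No document gives a number of late scans, so k below is an assumption.

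**1. The plan's own figures.** Power = P(|T| > t(0.975, N−2)), where T is noncentral t with N−2 degrees of freedom and noncentrality d√N/SD. The stated SD is used as the SD of the within-patient difference. The smallest even N for the six rows of Table 7.7:1 is 52, 68, 74, 98, 74 and 98, which matches every row. At N = 74, d = 2.5 and SD = 7.5, the noncentrality is 2.5 × 8.602 / 7.5 = 2.867 and power is 80.8%.

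**2. Late second scans.** Assume that the scan fully reflects the other drug. Both of that patient's on-treatment scans are then on the same drug and the expected difference is 0. With k such patients the expected contrast is 2.5 × (74 − k)/74. If the scans are set to missing, and only complete pairs are counted, the contrast stays at 2.5 with N = 74 − k.

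| k | Kept: contrast | Kept: power | Missing: contrast | Missing: power |
|---|---|---|---|---|
| 2 | 2.43 | 78.6% | 2.5 | 79.7% |
| 4 | 2.36 | 76.3% | 2.5 | 78.5% |
| 6 | 2.30 | 73.9% | 2.5 | 77.3% |

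The kept columns hold the SD at 7.5. Adding the variance from mixing the two kinds of patient, SD² = 7.5² + f(1 − f) × 2.5² with f = k/74, lowers power slightly further, to 78.5%, 76.1% and 73.5%.

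**3. Late third scans.** Assume that the whole drug effect is gone. Borrow 3.63 for fluticasone/salmeterol (B) against no treatment. With a true difference of 2.5, tiotropium/olodaterol (A) then loses 3.63 + 2.5 = 6.13.

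- In sequence AB the third scan belongs to B. Each one raises the A − B contrast by 3.63/74 = 0.049.
- In sequence BA it belongs to A. Each one lowers the contrast by 6.13/74 = 0.083.

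For 4 such scans:

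- all in AB: 2.5 + 4 × 0.049 = 2.70
- all in BA: 2.5 − 4 × 0.083 = 2.17
- two in each: 2.5 + 2 × 0.049 − 2 × 0.083 = 2.43

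An even split does not cancel, because the two treatments lose different amounts.

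**The case against.** **The endpoint definition may already exclude these scans.** Protocol 5.1.1 ties the value to the week before the visit, SAP 5.1 adopts it, and SAP 6.7 repeats the sixth week. This is the best counter-argument, but it does not settle the matter. F3 treats the late scan as a recorded endpoint value and bars it from one set only. The two texts need reconciling.

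**Final decisions are left to before database lock.** The table footnote says so. However, SAP 6.2 and 6.3 describe those decisions as concerning important violations and PPS membership.

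**The event should be rare.** The visit schedule makes the visit day the latest time for the CMR, visits can be rescheduled, and a delay for oral steroids or theophylline also postpones the lung function tests that follow. This stands. One route remains plausible: Protocol 4.2.1 postpones CMR by at least two days when antibiotics are given for a respiratory infection, and such a patient need not meet the exacerbation definition that FAS-EE uses.

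**The full-dilution model is too harsh.** This also stands. A reader might infer that a post-Visit 3 scan is simply on the other drug. Protocol 3.2 expects residual tiotropium effect for up to a couple of days in sequence AB. In sequence BA, active Respimat dosing begins only the next morning. After Visit 4, patients may return to their previous medication, so total loss of effect is likewise extreme.

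**Stronger readings.** A reader might infer that the 12-hour boundary in SAP 6.1 moves a late second scan into period 2. No rule does this for CMR, and it would give that period two scans. A reader might also infer that the F3 flag affects no analysis at all. Table 6.3:1 gives the PPS none, but some SAP sections are blacked out, so the claim should stop at the visible text.

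**Conclusion.** The gap is real. Nothing visible in the SAP keeps a scan dated after the switch, or after the end of treatment, out of the primary contrast, although such a scan does not fit Protocol 5.1.1.

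The size is uncertain and probably small. At 2 to 6 late second scans, the upper-bound dilution is 0.07 to 0.20 mL/m² on a true 2.5. The power lost compared with setting the scans to missing is 1.1 to 3.4 percentage points. Four late third scans could move the contrast to anywhere from 2.17 to 2.70, also as an extreme case. All of this rests on assumed counts and on full loss or full replacement of the drug effect.

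The documents do not support saying that the primary result will be materially distorted. They support saying that the plan leaves an avoidable bias open, in a direction that for third scans depends on sequence. Severity is low to moderate.

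**What to change.** Add to SAP 6.6 or 6.7, to be applied before FAS and FAS-EE assignment and before unblinding:

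*A second CMR dated after Visit 3, or a third CMR dated after Visit 4 (F3, conditions B2 and B3), does not meet the endpoint definition. It is set to missing for that period in all CMR efficacy analyses, including FAS-EE, and is not reassigned to another period.*

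Keep F3 as the important-violation flag. Use F3's own visit-date boundary, not the 12-hour limit in SAP 6.1: that limit allocates time to periods and does not match F3's date and 1-to-8-hour conditions.

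The cost is two sentences and one programming condition on dates already collected. A few scans may be lost, and SAP 6.6 already leaves completely missing visits to the mixed model.
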